20.0 Study Monitoring, Auditing and Inspecting

20.1 Auditing and Inspecting

By submitting this study for review, you agree to the following statement – DO NOT ALTER OR DELETE:

The investigator will permit study-related monitoring, audits, and inspections by the Penn State quality assurance program office(s), IRB, the sponsor, and government regulatory bodies, of all study related documents (e.g., source documents, regulatory documents, data collection instruments, study data etc.). The investigator will ensure the capability for inspections of applicable study-related facilities (e.g., pharmacy, diagnostic laboratory, etc.).

21.0 Future Undetermined Research: Data and Specimen Banking

If this study is collecting identifiable data and/or specimens that will be banked for future undetermined research, please describe this process in the sections below. This information should not conflict with information provided in section 9.1.1 regarding whether or not data and/or specimens will be associated with identifiers (directly or indirectly).

21.1 Data and/or specimens being stored

Identify what data and/or specimens will be stored and the data associated with each specimen.

All data will be handled in accordance with the consent procedures and IRB protocol. Identifiers will be stripped from the data files for archival storage. Identifying information will be destroyed within three years of the end of the project.

21.2 Location of storage

Identify the location where the data and/or specimens will be stored.

Archival data will be stored on SharePoint, PSU's secure cloud file transfer server.

21.3 Duration of storage

Identify how long the data and/or specimens will be stored.

De-identified study data will be archived indefinitely. Identifying info will be destroyed within three years of the end of the project.

21.4 Access to data and/or specimens

Identify who will have access to the data and/or specimens.

Only the research team will have access to archival data.

21.5 Procedures to release data or specimens

Describe the procedures to release the data and/or specimens, including: the process to request a release, approvals required for release, who can obtain data and/or specimens, and the data to be provided with the specimens.

Identifying information will not be released. Only members of the research team will have access to archival data.

21.6 Process for returning results

Describe the process for returning results about the use of the data and/or specimens.

N/A

Evaluation of the Research to Policy Collaboration Model

NCT03671434

September 16, 2021

Statistical Analysis Plan

Sample Size Justification

Statistical analyses are all powered at least at a 90% level to detect effect sizes of 0.2 or greater (power analysis conducted with *Optimal Design plus Empirical Evidence*).

We aim to enroll a maximum of 300 researchers in the baseline period of this study. The target number of study participants in the full study is 80, including 40 researchers in the intervention and 40 researchers in the control group. This level of oversampling is required because not all researchers will complete all phases of the intervention and oversampling will combat attrition from study participation.

It is anticipated that around 300 researchers will be recruited for the RPC. We believe that at least $\frac{3}{4}$ ($n = 225$) of those may participate in the study at baseline, and approximately half of those individuals may complete the study ($n = 112$), which would over-sample for the current study.

Data Quality Plan

Participants will fill out the surveys directly, minimizing possible errors associated with manually entering data. The surveys will be deployed through *REDCap*, which has integrated data quality procedures, such as an approval routing process for any changes to an active survey to ensure it will not remove or alter existing data. The legislative coding will be completed by trained coders who meet an acceptable level of reliability ($\alpha = .70$). Thirty percent of the sampled legislation will be double-coded to ensure high-quality and reliable data.

Missing data will be handled with multiple imputation because this is best practice when data are not missing at random. This method will be guided by Lee and colleagues' approach to multiple imputation for multilevel data, which reduces and checks for biases in imputed estimates (e.g., tests for convergence and model fit) and suggests that there must be at least 50% complete data and incorporating auxiliary variables highly correlated with the imputed variable (e.g., outcome variables assessed at prior time points).

Data Analysis Plan

All data will be handled in accordance with the consent procedures and IRB protocol. Identifiers will be stripped from the data files for archival storage. Identifying information will be destroyed within three years of the end of the project. De-identified study data will be archived indefinitely. Identifying info will be destroyed within three years of the end of the project.

Analyses for survey outcomes for researchers and legislative staff follow similar patterns and will be conducted in *MPlus* or *SAS*. For researchers, logistic models will be used to model researchers' change from baseline in 1) knowledge of current lobbying restrictions, 2) belief that engaging with policymakers would improve their own research, and 3) level of policy engagement. For legislative staff, generalized linear models will be used to model the trial groups on how much congressional offices value URE for 1) conceptual, 2) instrumental, and 3) tactical purposes

For legislative offices, we will assess the impact of the RPC on both proposed and enacted bills. Since the continuity of relevant legislative activity may be inconsistent between short intervals due to Congressional recesses (e.g., 3-month survey timeframes), legislative activity will be analyzed and compared between two time periods: one-year before RPC implementation (baseline) and six months following RPC implementation (post-assessment). The indicators for evidence use in this

project will reflect having used research evidence language in legislation related to the wellbeing of children and families, as determined by trained coders, on which the office is listed as a sponsor or original cosponsor. This outcome is dichotomous: did or did not sponsor or originally cosponsor legislation that was coded as having used research evidence. Therefore, logistic regression analyses will assess use of research evidence. Given the cyclical nature of Congress, it is expected that overall legislative productivity will be different at baseline than at the post-assessment. Thus, the control and intervention groups will be compared to one another at each timepoint separately. They will be compared at baseline to establish if there is a difference in sample, perhaps due to self-selection biases. If there is no difference at baseline, we will compare the use of research evidence in legislation among control offices and intervention offices at the post-assessment time period. We will regress dichotomous post-assessment use of research evidence on group assignment. Similar logistic regressions will be conducted on the probability of an office writing 1) a bill related to the wellbeing of children and families and 2) a bill that did not include URE research evidence terms.

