3.3 Early Withdrawal of Subjects

3.3.1 Criteria for removal from study

Insert subject withdrawal criteria (e.g., safety reasons, failure of subject to adhere to protocol requirements, subject consent withdrawal, disease progression, etc.).

Researchers who choose to stop participating in the study or the RPC itself. All study participants can choose to opt-out of the study at any time.

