3.3.2 Follow-up for withdrawn subjects

Describe when and how to withdraw subjects from the study; the type and timing of the data to be collected for withdrawal of subjects; whether and how subjects are to be replaced; the follow-up for subjects withdrawn from investigational treatment.

No follow-up will be conducted with withdrawn subjects.

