7.0 Study Design and Procedures

7.1 Study Design

Describe and explain the study design.

This human subjects research involves a longitudinal randomized controlled trial and depth interviews of researchers who participate in the Research-to-Policy Collaboration (RPC). Researchers are recruited to participate in the RPC. When a researcher voluntarily enlists in the RPC, they provide information about themselves and their expertise as part of RPC implementation. Subsequently, RPC participants are invited to participate in the study. Those who agree to participate are randomly assigned to either the RPC intervention group or a blinded control group that receives a “light touch” intervention. The next step of RPC implementation involves creating a discussion forum for engaging researchers in training or policy efforts. Different discussion forums will be used for each group: the RPC group (including those in the study who were assigned the intervention as well as those who refused to participate in the study) and the control group. The control group will receive information sheets regarding how to engage in policy, whereas the RPC group will be actively engaged in a series of six voluntary one-hour webinars preparing researchers for policy engagement, and will receive solicitations for contributing to policy efforts via the discussion forum. These activities are designed to build researchers’ capacity for successful collaborative interactions with congressional staff around *current policy priorities* and *specific, time-sensitive needs* of congressional offices.

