7.2.2 EXAMPLE: Visit 2 or Day 2 or Post-test, etc. (format accordingly)

Provide a description as defined above and format accordingly.

The same survey protocol as used in the pre-test will be administered approximately every three months for about one year: (2) Subsequent to training, (3) Subsequent to policy engagement, and (4) Follow-up. Efforts to minimize survey attrition will include tracking non-responses to follow-up surveys and requesting survey participation via individual emails twice per week until survey completion or until the 3-week window for survey participation ends or until the participant opts-out of participating in the survey. In the last week of the survey window, survey participants who have not yet participated or opted-out of participation will be contacted by phone to request their participation and to complete the survey over the phone if needed.

Qualitative interviews will occur subsequent to the RPC implementation, approximately 9 months following study enrollment, using web-chat or phone. These interviews will ask:

- How did you become involved in the RPC? Is this your first involvement with policy? With legislation? If no, what are your previous experiences?

- What were your expectations and aspirations from involvement in the RPC?
- Can you describe the interactions you've had with policymakers through the RPC? (e.g. informal coffees, phone calls, formal meetings, etc). How does this compare to interactions outside the RPC?
- What kinds of evidence have you seen and used as part of the RPC? How? Did this reflect your expectations?
- What has worked well? What could have gone better? (Risks of interaction, perceptions and stereotypes)

This study also involves non-human research data, drawing from public information regarding public officials' use of research evidence, which will be obtained from legislators' sponsored bills, public statements, and reported research use by public officials. Non-human research data will also support the interpretation of key findings from the current investigation that involve human subjects.

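### Multiple imputation is justified by data being not missing at random, but the method described assumes missing at random, and no missing-data sensitivity analysis is planned

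*SAP*

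**What the plan says.** The SAP (Data Quality Plan) gives this reason for its method: "Missing data will be handled with multiple imputation because this is best practice when data are not missing at random". It then names a published approach to imputing multilevel data as its guide, "which reduces and checks for biases in imputed estimates (e.g., tests for convergence and model fit" being the examples it gives. That approach is said to call for at least 50% complete data and for "incorporating auxiliary variables highly correlated with the imputed variable (e.g., outcome variables assessed at prior time points". Protocol section 8.3 adds only that multiple imputation will be used, with change modelled over four surveys.

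On the amount of missing data, the SAP (Sample Size Justification) expects 225 researchers at baseline, of whom "approximately half of those individuals may complete the study" (n = 112).

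On how data come to be missing, Protocol section 3.3.1 lists as grounds for removal "Researchers who choose to stop participating in the study or the RPC itself", and section 3.3.2 says "No follow-up will be conducted with withdrawn subjects". Non-responders who have not opted out are emailed and, in the last week of the survey window, "will be contacted by phone to request their participation and to complete the survey over the phone if needed" (section 7.2.2).

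Policy engagement is a primary endpoint (Protocol section 1.2) and one of the three researcher outcomes that the SAP's Data Analysis Plan assigns to logistic models of change from baseline.

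**The concern.** Imputation from observed auxiliaries and earlier responses recovers the right answer if, given those variables, people who do not respond have outcomes like those who do. That is the missing-at-random assumption. If data are truly not missing at random, the same procedure is biased unless it includes an explicit shift, selection or pattern-mixture component, and none is specified. The stated reason therefore contradicts the method.

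The named checks do not fill the gap. Convergence and model fit are judged on observed data and cannot detect a departure that lives in the unobserved values.

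A departure tied to the outcome is plausible here, though not shown. A researcher who stops the RPC can be removed and not followed, and policy engagement is itself an outcome. The arms also receive very different amounts of contact: the RPC arm "will be actively engaged in a series of six voluntary one-hour webinars preparing researchers for policy engagement" and is solicited for policy work, while controls receive information sheets. If the departure, or the missing fraction, differs by arm, the treatment effect is biased, and the direction cannot be known in advance.

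**Working it through.** **1. The plan's own figure.** 300 × 3/4 = 225 at baseline; 225 × 1/2 = 112.5, given as 112. The figure reproduces.

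**2. Missing fraction.** If completing means answering the last survey, and all 225 are analysed, (225 − 112)/225 = 113/225 = 50.2% is missing there. The documents give no figures for the surveys in between. Assuming a straight-line decline:

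| Survey | Responding | Missing |
|---|---|---|
| Baseline | 225 | 0% |
| 2 | 187.3 | 16.7% |
| 3 | 149.7 | 33.5% |
| 4 | 112 | 50.2% |

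Over all participant-surveys, 674/900 = 74.9% are complete (about 25% missing). After baseline, 449/675 = 66.5% are complete (33.5% missing).

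**3. Bias on the risk-difference scale.** Let m be the missing fraction in an arm and d the gap between the true and imputed risk among non-responders. The error in the treatment difference has size m₁d₁ − m₀d₀. With equal m in both arms this is m × (d₁ − d₀). The gaps are assumptions:

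| Between-arm gap (points) | m = 25% | m = 33.5% | m = 50.2% |
|---|---|---|---|
| 5 | 1.3 | 1.7 | 2.5 |
| 10 | 2.5 | 3.4 | 5.0 |
| 20 | 5.0 | 6.7 | 10.0 |

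**4. Bias on the odds-ratio scale, which the logistic models use.** Assume imputed risks of 50% (RPC) and 40% (control), so the imputed odds ratio is (0.50/0.50)/(0.40/0.60) = 1.50. If the non-responders in an arm differ from what is imputed by δ on the log-odds scale, that arm's overall risk is (1 − m)p + m × expit(logit(p) + δ).

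Example: m = 0.502, RPC arm only, δ = −0.8. Risk = 0.498 × 0.50 + 0.502 × 0.310 = 0.405. Odds ratio = (0.405/0.595)/(0.40/0.60) = 1.02.

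| Departure | δ = −0.8 | δ = −0.4 | δ = +0.4 | δ = +0.8 |
|---|---|---|---|---|
| RPC only, m = 25% | 1.24 | 1.36 | 1.66 | 1.81 |
| RPC only, m = 33.5% | 1.16 | 1.31 | 1.71 | 1.94 |
| RPC only, m = 50.2% | 1.02 | 1.23 | 1.83 | 2.21 |
| Control only, m = 50.2% | 2.18 | 1.82 | 1.22 | 1.00 |
| Both equally, m = 50.2% | 1.48 | 1.49 | 1.49 | 1.48 |

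**5. A simulation of imputation of this kind.** Assumptions: a continuous outcome with SD 1, 112 per arm at baseline, about 50% missing, baseline outcome as the auxiliary with correlation 0.6, 20 imputations and 1,000 replicates. Where response depended on the outcome, its log-odds changed by 0.5 to 1.0 per SD.

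- Missing at random: bias −0.01 to 0.00; 95% interval coverage 92% to 95%.
- Not at random, alike in both arms: bias −0.03 to 0.00; coverage 93% to 96%.
- Not at random in the intervention arm only: bias +0.15 to +0.29 SD; coverage 83% down to 53%.

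For scale, the SAP's target effect size is 0.2. The planned models are logistic, so these results support the pattern rather than predict the trial's bias.

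**6. Search of both documents.** Neither contains a delta adjustment, tipping-point, pattern-mixture, selection-model or complete-case analysis, or any other missing-data sensitivity analysis.

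**The case against.** The strongest reply is that the authors meant not missing *completely* at random. Imputation is then a reasonable choice and the contradiction is a slip of wording. The SAP never names the mechanism its imputation model assumes, the checks are introduced only as examples, and the guiding approach cannot be seen here and may ask for more. All of this is fair. It softens the first half of the point but leaves the second: nothing in either document goes beyond missing at random.

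Several design features favour similar response in the two arms. Controls are blinded, the webinars are voluntary so skipping one is not withdrawal, all non-responders are pursued in the same way, and every completed survey is paid. These may reduce missingness or keep it balanced, but they do not test the assumption.

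The sizes also need care. The 50.2% case has 112/225 = 49.8% complete, at or just under the SAP's own 50% condition, and the SAP does not say whether that condition applies by survey, by variable or overall. The 25% average includes baseline, so it matches no follow-up contrast; the 33.5% rows are the better middle case. Every departure and risk is assumed.

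Finally, the point concerns survey outcomes. The legislative outcomes come from public records and do not depend on survey response.

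**Conclusion.** The concern holds and should be fixed. As written, the SAP's reason for multiple imputation does not fit the method it describes, and no planned analysis would show how far the researcher survey results rest on missing at random.

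The exposure is up to about half of outcomes at the last survey (50.2%), provided that completing means answering that survey and that all 225 baseline participants are analysed. On assumed risks of 50% and 40%, a departure of up to 0.8 log-odds in the RPC arm alone moves an odds ratio of 1.50 to between 1.02 and 2.21 at 50.2% missing, or between 1.16 and 1.94 at 33.5%. Equal departures with equal missing fractions leave it almost unchanged. These figures show what is possible. They are not evidence that bias exists, and the documents do not establish that dropout differs by arm. Confidence is high in the textual finding; the sizes are illustrative.

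**What to change.** 1. Correct the sentence in the Data Quality Plan so that it says the primary imputation assumes data are missing at random given arm, baseline and all observed surveys. Impute by arm. If about 56 completers per arm (112/2, with equal allocation) is too few for stable separate models, a single model with arm and arm-by-earlier-outcome terms is an alternative.
2. State the binary coding of each researcher outcome. Then pre-specify a delta-adjusted analysis on the log-odds scale of the planned models. Vary the shifts in both directions and separately by arm, widen them until the conclusion changes, and report the shift at which it does.
3. Report missingness by arm and survey beside the primary result, and say how the 50% completeness condition is applied.

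The cost is SAP wording and a few extra model runs, with no new data. The drawback is that the robustness statement may turn out less favourable.

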1.2 Primary Study Endpoints

State the primary endpoints to be measured in the study. Clinical trials typically have a primary objective or endpoint. Additional objectives and endpoints are secondary. The endpoints (or outcomes), determined for each study subject, are the quantitative measurements required by the objectives. Measuring the selected endpoints is the goal of a trial (examples: response rate and survival).

This study will measure changes in participants' policy knowledge and skills, policy engagement, and the extent to which research activities are informed by public officials' needs.

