3.1 Inclusion Criteria

List the criteria that define who will be included in your study.

Researchers who voluntarily enlist in the RPC will be asked to participate in the trial. All participants will be over 18 years old.

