8.0 Subject Numbers and Statistical Plan

8.1 Number of Subjects

Indicate the total number of subjects to be accrued.

If applicable, distinguish between the number of subjects who are expected to be enrolled and screened, and the number of subjects needed to complete the research procedures (i.e., numbers of subjects excluding screen failures.)

We aim to enroll a maximum of 300 researchers in the baseline period of this study. The target number of study participants in the full study is 80, including 40 researchers in the intervention and 40

researchers in the control group. This level of oversampling is required because not all researchers will complete all phases of the intervention and oversampling will combat attrition from study participation.

Twenty-two researchers from the intervention group will be selected to participate in depth-interviews (11 at pre-test and 11 at post-test). Researchers will be sampled purposively such that the sample is representative of those with or without prior policy experience and range in their attitudes toward policy engagement (e.g., skeptical or positive), which will be determined by survey data from the first time point.

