8.3 Statistical methods

Describe the statistical methods (or non-statistical methods of analysis) that will be employed.

Surveys data will be analysed longitudinally by modelling change across 4 time points—including repeated measures and multilevel growth curve models (MLM) using *MPlus*. Missing data will be handled with multiple imputation.

Qualitative interview data will be analyzed using a thematic process followed by an intensive discourse analysis. Data will be interpreted alongside observational data using an interpretive policy analysis to develop a data-driven theoretical framework for describing evidence use in the RPC.

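### The SAP's logistic model of researchers' change from baseline leaves the event undefined, differs from the protocol's growth models, and would waste information if the event is improved versus not improved

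*SAP*

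**What the plan says.** The SAP's Data Analysis Plan covers the researcher outcomes in one sentence: "logistic models will be used to model researchers' change from baseline in 1) knowledge of current lobbying restrictions", followed by "belief that engaging with policymakers would improve their own research, and 3) level of policy engagement". It names no event, cut-point, item scale, follow-up survey or covariate, and no rule for respondents already at the top at baseline.

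Protocol section 8.3 describes the analysis of the same surveys as "modelling change across 4 time points", by repeated-measures and multilevel growth curve models. Section 1.2 words the endpoints as changes, with no dichotomy: "This study will measure changes in participants' policy knowledge and skills, policy engagement", and the extent to which research is informed by officials' needs.

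Elsewhere the SAP defines a yes/no outcome explicitly. For the legislative analysis it says "This outcome is dichotomous: did or did not sponsor or originally cosponsor legislation" coded as using research evidence, and gives that as the reason for logistic regression. For legislative staff it names generalized linear models for how much offices value research use.

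**The concern.** A logistic model whose subject is change suggests an event of the form improved or not improved. The SAP supports that reading by tying logistic regression to a dichotomous outcome in the legislative section. A belief and a level of engagement read as graded measures. If they are cut to improved or not, three things follow by logic:

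- a one-step and a four-step gain count the same;
- a decline counts the same as no change;
- a respondent in the top category at baseline can never be an event, whichever arm they are in.

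The trial targets 80 participants and expects about 112 completers, so it has little room to lose information. Leaving the event open also allows the scoring rule to be chosen after the data are seen. Finally, the two documents describe different models for the same surveys, so a reader cannot tell which one yields the reported effect.

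**Working it through.** **The plan's own power figure.** The SAP says "Statistical analyses are all powered at least at a 90% level to detect effect sizes of 0.2 or greater". The metric and alpha are not given; I assume a standardized difference and two-sided 5%. Power = Φ(d / √(2/n) − 1.96). With d = 0.2 and n = 40 per arm: 0.2 / 0.2236 = 0.894, and Φ(0.894 − 1.96) = 14%. With 56 per arm (112 completers split 1:1) it is 18%. For 90% power, n = 2 × (3.2415 / 0.2)² = 526 per arm. Averaging three follow-ups with baseline adjustment gives 27% to 72% at 40 per arm (correlation 0.3 to 0.9). Reading 0.2 as a risk difference, a correlation or Cohen's f gives 43% to 61%. The stated figure is therefore not reproduced at the target size under any of these readings. That is a separate problem, but it bears on how much loss the design can absorb.

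**Inputs for the comparison.** From the documents: 112 expected completers and 40 per arm (SAP, Sample Size Justification). Assumed, because the documents do not give them: a five-category item, a latent normal score with baseline to follow-up correlation 0.5, 10%, 20% or 40% in the top category at baseline with the rest spread evenly, a shift of 0.2 or 0.5 SD in the RPC arm, and one follow-up. Two million simulated records per setting supply the event rates, the adjusted difference and its SD.

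**Formulas.** Improved yes/no: power = Φ{(p1 − p0 − 1.96·√[2p̄(1 − p̄)/n]) / √[(p0(1 − p0) + p1(1 − p1))/n]}. Baseline-adjusted score: power = Φ(Δ / (SD·√(2/n)) − 1.96).

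**One case in full** (20% at top, 0.5 SD, n = 56 per arm).

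- Improved: p0 = 0.339, p1 = 0.511, p̄ = 0.425. The null standard error is √(2 × 0.425 × 0.575 / 56) = 0.0934 and the alternative one is 0.0920. Power = Φ((0.172 − 0.1831) / 0.0920) = Φ(−0.12) = 45%.
- Adjusted score: Δ = 0.652, SD = 1.229, standard error 1.229 × 0.189 = 0.232. Power = Φ(2.81 − 1.96) = 80%.

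**All cases** (n per arm is for 90% power).

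| Shift | At top | n per arm, improved v score | Ratio | Power at 56 per arm | Power at 40 per arm |
|---|---|---|---|---|---|
| 0.2 SD | 10% | 922 v 458 | 2.0 | 12% v 20% | 10% v 16% |
| 0.2 SD | 20% | 1036 v 476 | 2.2 | 11% v 20% | 9% v 15% |
| 0.2 SD | 40% | 1718 v 545 | 3.2 | 8% v 18% | 7% v 14% |
| 0.5 SD | 10% | 147 v 74 | 2.0 | 51% v 81% | 39% v 67% |
| 0.5 SD | 20% | 171 v 75 | 2.3 | 45% v 80% | 34% v 66% |
| 0.5 SD | 40% | 310 v 89 | 3.5 | 28% v 73% | 21% v 58% |

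**How the ceiling acts.** With 20% at the top and a 0.2 SD shift, improvement among those able to improve is 42.5% v 51.1%. Counting everyone gives 0.8 × 42.5% = 34.0% v 0.8 × 51.1% = 40.9%, so the difference shrinks from 8.6 to 6.9 points.

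**With almost no ceiling.** A separate simulation (3000 trials per setting, 5% at the top, correlation 0.5 to 0.7, 0.5 SD, 112 in total) gave 55% to 73% for improved against 80% to 91% for the adjusted level. Much of the loss therefore comes from dichotomising change, not only from the ceiling.

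**The case against.** The strongest reply is that the SAP contains no responder rule. A reader might infer that the plan scores anyone at the top of the scale as a failure, but no text says so. A cumulative-logit model, a logistic model of follow-up status adjusted for baseline, or a repeated-measures logistic model with a group-by-time term would not do this, and the wording excludes none of them. The sentence may also be shorthand for the growth models in Protocol 8.3. This stands, so the loss is conditional on the event being improved or not. It does not remove the lack of definition or the mismatch between the documents.

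The item scales cannot be seen either. Protocol 7.2.1 places the instruments in a separate supporting document. Lobbying knowledge could be scored right or wrong, in which case no size of change is lost. This stands too.

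A reader might take Protocol 8.1, where "the sample is representative of those with or without prior policy experience and range in their attitudes toward policy engagement", as evidence that many trial participants start at the ceiling. It is not. That sentence describes 22 purposively chosen interviewees, and their attitudes are expected to run from skeptical to positive. Section 3.1, "Researchers who voluntarily enlist in the RPC will be asked to participate in the trial", shows interest in policy work, not top scores on knowledge or engagement. The share at the top is unknown and is treated above only as an assumption.

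Three further limits stand. At a 0.2 SD shift neither analysis has adequate power, so changing the model does not rescue the design at that effect. The SAP does not call these three outcomes primary, and the belief item is not clearly the third endpoint of section 1.2. A claim that chance baseline differences would bias the comparison would need an unadjusted model, and the SAP is silent on covariates.

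**Conclusion.** The point holds in conditional form. As fact, the SAP names a logistic model for change without defining event, scale, time point or baseline handling, and it does not match Protocol 8.3. If the event is improved versus not improved, which is the most natural reading, graded items lose the size of change, declines are merged with no change, and respondents at the top cannot be events.

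The size rests on the assumed five-category item, correlation 0.5, 10% to 40% at the top and one follow-up. On those inputs the required sample size is about 2 to 3.5 times that of a baseline-adjusted score. The power lost at 56 per arm is large for a 0.5 SD shift. For a 0.2 SD shift both analyses are weak. The documents do not establish that a ceiling exists in this population. The change should be made because it is cheap and the possible loss is large, and no passage justifies the logistic change form.

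**What to change.** In the SAP's Data Analysis Plan:

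- State each item's scale and, where an outcome is binary, its event.
- For graded items, replace the logistic change model with the full-scale outcome in a proportional-odds or linear longitudinal model using all four surveys. Include arm, time, arm-by-time and the baseline level of the same item (baseline as covariate, the three later surveys as outcomes). Name the follow-up contrast that carries the conclusion.
- For truly binary items, model follow-up status with baseline status as a covariate.
- Keep percent improved as a descriptive summary only.
- Bring this text and Protocol 8.3 into agreement, so that one model is named for the researcher surveys.

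The cost is wording. The surveys stay the same, and the software already named can be kept. The small downside is that a common odds ratio or mean difference is less immediate to readers than a percent improved, which can still be shown alongside.
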